## **4. SELECTION OF SUBJECT POPULATION**

### **4.1 Investigators**

Patients will be recruited by the specialists working at the Tatarstan Cancer Center in Kazan and at the Republican State Clinical Oncological Dispensary in Ufa.

## **4.2 Inclusion criteria**

The subject population must fulfil all of the following criteria:

1. The voluntary obtained informed consent signed by both the subject and the investigator.
2. Females 18 years age or more.
3. Histologically confirmed BC with known hormone receptors and HER2neu receptors status, Grade of tumor, diagnosed before enrolment into the study.
4. Availability of FFPE tissue samples received prior to any type of antitumor treatment start. Tumour tissue samples must be satisfied IHC requirements for PD-L1 testing.
5. Ability of blood samples receiving for NGS germline mutations testing.
6. Completed medical records (stage, receptors status, demographic data)

## **4.3 Exclusion criteria**

1. Any evidence of uncontrolled system pathology, active infections, active bleeding diathesis, renal graft, including virus hepatitis B, C or HIV.
2. Patients participating in clinical studies
3. Any medical condition, which on the opinion of the investigator may interfere the patient's participation in the study. The decision of patient exclusion can be made based on corresponding section in medical records (which must be completed prior to the visit in line with local standard) or on a visit information. It can include but not limited any medical conditions impeding sign informed concerns (for example mental disorder).

## **5. DISCONTINUATION OF SUBJECTS**

### **5.1 Criteria for Discontinuation**

Subjects may be discontinued from the NIS at any time. Specific reasons for discontinuing a subject from this NIS are:

1. Voluntary discontinuation by the subject who is at any time free to discontinue his / her participation in the NIS, without prejudice to further treatment
2. Incorrect enrolment e.g., the patient does not meet the required inclusion/exclusion criteria for the study.

## **5.2 Procedures for discontinuation**

Subjects who discontinue should be asked about the reason(s) for their discontinuation. If possible, they should be seen and assessed by the investigator according to current practice.

## **6. THERAPEUTIC STRATEGY**

### **6.1 Therapeutic strategy of a Non-Interventional Study**

The assignment of a subject to a particular therapeutic strategy is not decided in advance by a protocol but falls within current practice.

## **7. STUDY CONDUCT**

### **7.1 Restrictions during the study**

No specific restrictions are applicable for this non-interventional study.

## **8. MEASUREMENTS OF STUDY VARIABLES AND DEFINITIONS OF OUTCOME VARIABLES**

### **8.1 Primary variable**

PD-L1 expression in tumor and immune cells in FFPE tumor tissue samples estimated by ICH is the primary variable in this study. The primary variable value will be represented as “PD-L1 high” or “PD-L1 low”. PD-L1 expression for both TC and IC in the tumor microenvironment will be determined by the percentage of cells expressing PD-L1 at any intensity above background staining. PD-L1 will be defined as high if either  $\geq 25\%$  of TC or  $\geq 25\%$  of IC expressed PD-L1, and PD-L1 was defined as low if both  $< 25\%$  of TC and  $< 25\%$  of IC expressed PD-L1.

The following data to describe the primary objective will be collected:

The “PD-L1 high” cases rate in both patients with hereditary BC with pathogenic germline mutations in DNA-repair system genes and patients with sporadic BC without germline mutations in these genes.

### **8.2. Secondary variables**

The secondary variables for this study are defined as:

Patient characteristics:

- Age
- ethnicity (Tatar, Bashkir, Slavic etc)
- Family oncological history with pointed localization of cancer (BC, OC, Prostate cancer, Pancreatic cancer or other localizations) and relation degree
- Individual oncological history: BC, OC, pancreatic cancer or other localizations

Disease information/ diagnostic procedures:

- Disease stage and TNM classification
- Morphological classification, Grade (1/2/3)
- Receptor status: ER, PR, HER2neu
- Extent of the disease
- Profile of germline mutations in DNA-repair system genes
- Number of TILs
- PD-L1 expression in tumor and immune cells in FFPE tumor tissue samples estimated by ICH as “PD-L1 high” or “PD-L1 low” based on 50% cut-off. PD-L1 will be defined as high if either  $\geq$  50% of TC or  $\geq$  50% of IC expressed PD-L1, and PD-L1 was defined as low if both  $<$  50% of TC and  $<$  50% of IC expressed PD-L1.

## 9. SAFETY ASSESSMENT

### 9.1 Definitions

#### 9.1.1 Definition of an adverse event (AE)

“Adverse Event” or “AE” means a development of any untoward medical occurrence or the deterioration of a preexisting medical condition in a patient or clinical trial subject and which does not necessarily have a causal relationship with this treatment.

Adverse Event might be an unfavorable symptom (e.g. nausea, chest pain), factor (e.g. tachycardia, enlarged liver) or abnormal research result (e.g. deviation of laboratory rates, alteration of electrocardiogram) temporally associated with the use of a medicinal product, whether or not considered related to the medicinal product.

The following information should be reported: the use of medication during pregnancy (irrespectively of whether the pregnancy termination is known), and/or lactation, suicide and attempted suicide, suspected drug interactions.

### **9.1.2 Definition of serious adverse event (SAE)**

A SAE is an AE, occurring at any dose or study phase that fulfils one or more of the following:

- Results in death.
- Is life-threatening.
- Requires in-patient hospitalization or prolongation of existing hospitalization.
- Results in persistent or significant disability/incapacity or substantial disruption of the ability to conduct normal life functions.
- Is a congenital abnormality/birth defect?

Is an important medical event that may jeopardize the subject or may require medical intervention to prevent one of the outcomes listed above.

NOTE.

- The Term "threat to life" with respect to SAEs means that there was an immediate risk of lethal outcome in the patient at the time of this event. This definition does not refer to event which hypothetically could result in lethal outcome, in that case, that if it had occurred at more severe form.

Medical events that are important, but do not result in lethal outcome or events that are directly life-threatening or requiring hospitalization, can also be considered as serious adverse events in those cases when, in accordance with sound clinical or scientific opinions, it is hazardous for the patient (or patient) and when in order to prevent one of the outcomes mentioned above medical or surgical intervention may be required. In this case, the event is considered as serious. Examples of such events are common or malignant tumor, allergic bronchospasm requiring intensive therapy in the emergency care department or at home, hematological disorders or convulsions that do not result in hospitalization or the development of drug dependency or drug abuse.

## **9.2 Non-interventional studies without special safety assessment**

The active collection of any safety data will not be performed due to the non-interventional type of the study. Spontaneous reports of events related to safety will be reported in accordance with the pharmacovigilance regulatory requirements in the post-marketing period. It is imperative that all investigators participating in the study must be familiarized with this section of the Protocol. Primary investigator is responsible for training of co-investigators involved in the study upon the procedures of processing of spontaneously reported safety events, as well as with national pharmacovigilance regulatory requirements in Russia.

## **9.3 Non-interventional studies with special safety assessment**

The active collection of any safety data will not be performed due to the non-interventional type of the study.

## **9.4 Report on safety information**

### **9.4.1 Reports on adverse events**

Safety monitoring will be carried out in accordance with the local pharmacovigilance requirements, used in standard medical practice in the Russian Federation.

### **9.4.2 Reports on unexpected adverse reactions at drug administration**

Since it is not planned to research any study drug or vaccine, and monitoring of patients receiving standard therapy with drugs approved for use in the Russian Federation will be carried out. Safety monitoring and report of adverse events, including adverse reactions, not specified in the package inserts, will be performed in accordance with local pharmacovigilance requirements, applicable for standard medical practice in the Russian Federation.

### **9.4.3. Register of spontaneous reports of adverse events**

The following principles of AEs registration, reported for patients participating in the study, should be applied: the investigator must report AEs within the pharmacovigilance procedures and in accordance with local regulatory requirements:

1. To the Federal Service on Surveillance in Healthcare: In written form to address: [name]. Special form available at the moment on the following site should be used:  
<http://www.roszdravnadzor.ru/i/upload/files/1308641445.19876-26263.doc>.
2. To the correspondent pharmaceutical company, i.e. marketing company owning registration certificate on the correspondent drug, according to the local regulatory requirements.
3. In case if spontaneous AE is connected to the AstraZeneca drug, the investigator should submit information about AE to the Patient Safety department of AstraZeneca (in business and non-business hours) within 24 hours from the moment of adverse event information receipt via any of the following ways:
  - E-mail: [contact]
  - Send a message and /or fill (Attachment 4 to the protocol) the AE Reporting Form;
  - [contact], [contact].

## **10. ETHICAL CONDUCT OF THE NON-INTERVENTIONAL STUDY**

The Non-Interventional Study will be performed in accordance with ethical principles that are consistent with the Declaration of Helsinki, ICH GCPs.

The Investigator will perform the NIS in accordance with the regulations and guidelines governing medical practice and ethics in the country of the NIS and in accordance with currently acceptable techniques and know-how.

## **10.1 Ethics review**

The final protocol of the Non-Interventional Study, including the final version of the Subject Informed Consent Form, must be approved or given a favourable opinion in writing by the Local Ethics Committee.

The Local Ethics Committee must also approve any amendment to the protocol and all advertising used to recruit subjects for the study, according to local regulations.

### **10.1 Subject Informed consent**

The Investigator at each site will ensure that the subject is given full and adequate oral and written information about the nature, purpose, possible risk and benefit of the NIS. Subjects must also be notified that they are free to discontinue from the NIS at any time. The subjects should be given the opportunity to ask questions and allowed time to consider the information provided.

The signed and dated subject informed consent must be obtained before any specific procedure for the NIS is performed, including:

- Interview with the investigator
- Fulfil the questionnaires
- CRFs completion.

The Investigator must store the original, signed Subject Informed Consent Form. A copy of the signed Subject Informed Consent Form must be given to the subject.

## **10.2 Subject data protection**

The Subject Informed Consent Form will incorporate wording that complies with relevant data protection and privacy legislation. Pursuant to this wording, subjects will authorise the collection, use and transmission of their personal data by the Investigator and by those persons who need that information for the purposes of the NIS.

The Subject Informed Consent Form will explain that NIS data will be stored in a computer database, maintaining confidentiality in accordance with the local law for Data Protection.

# **11. STUDY MANAGEMENT**

## **11.1 Monitoring, Quality Control and Archiving**

The sponsor will carry out Monitoring and quality control in each centre to:

- Provide information and support to the investigator(s)

- Confirm that the research team is complying with the protocol and that data are being accurately recorded in the case report forms (CRFs)
- Ensure that the subject informed consent forms are signed and stored at the investigator's site
- Ensure that the CRFs are completed properly and with adequate quality.

## **11.1 Training of study site personnel**

Investigators should be trained in conduction of the study. New information about the study should be timely given to doctors.

Investigators should be trained in the local regulatory pharmacovigilance procedures requirements. If information about AE, emerged against the background of the use of any investigational drug or vaccine becomes known to Investigator, Investigator must collect and transmit such information to mentioned above contacts within the time-frames regulated by local pharmacovigilance requirements.

## **11.1 NIS timetable and end of study**

Before the first subject is enrolled in the NIS and any NIS related procedures are undertaken the following should be fulfilled

- Written approval of the NIS by the Ethics Committee and/or Regulatory Authorities, according to local regulations

**The planned timetable for the NIS is estimated to be as follows:**

First subject in	January 2018
Last subject in	January 2019
Study Database lock	March 2019
Final Study Report	July 2019

## **12. DATA MANAGEMENT**

### **12.1 Collection, monitoring, processing of data and archiving**

Each enrolled patient would be assigned with unique identification number (the least available from the pre-designed sequence). The individual Case Report Form (CRF), specially designed for this study, will be completed for each patient enrolled.

The collection of data from out-patient medical records or disease histories for hospitalised patient, as well as collection of data received by a physician during the routine patient examination will be performed. Any special data collection procedures are not stipulated within the framework of this study. All patient data will be recorded by the participating physician both in the source documents and in the CRF. Source documents are kept by physician.

Signed Informed Consents will be kept by the physician during the study and after the study completion.

Database will have to be completed, and then passed appropriate quality check, considered to be full and accurate, and then will be locked. Collected data will be analyzed.

Essential study documents must be retained by the participating physician for as long as needed to comply with local and international regulations. No source documents, containing patients' personal data, should be taken away from the physician.

### **12.2 Reporting and publication of data**

- Investigators will prepare a Non-Interventional Study Report within 6 months after completion of the last subject.
- The results from the NIS will be presented to the Investigators as a Study report at Q4, 2019.

In accordance with the Declaration of Helsinki, both authors and publishers have ethical obligations. In publication of the results of the NIS, the authors are obliged to preserve the accuracy of the results. Negative as well as positive results should be published or otherwise publicly available.

## **13. STATISTICAL METHODS AND SAMPLE SIZE DETERMINATION**

### **13.1 Statistical evaluation – general aspects**

This is prospective non-interventional study designed as a case-control type for exact assessment of influence of the mutations in DNA repair genes presence on PD-L1 expression in BC. Case-control studies are often used for comparison of influence a predictive factor on a outcome. The primary variable (PD-L1 expression) and explored risk factor (mutations in DNA repair genes presence) will have nominal value: high/low and yes/no respectively.

A Non-Interventional Study is a study in which epidemiological methods including other methods that can be used to analyse human population health data.

All statistical analyses will be performed by means of the statistical software system.

A comprehensive Statistical Analysis Plan will be prepared before database lock.

### **13.2 Description of outcome variables in relation to objectives and hypotheses**

The following measures will be analyzed:

- Proportion and number of PD-L1 high cases in investigational group.
- Proportion and number of PD-L1 high cases in control group.
- Proportion of PD-L1 high cases in different morphological variants patient's subgroups.
- Proportion of PD-L1 high cases in different receptor status (ER, PR, HER2neu) patients subgroups.
- Number of TILs in depends on germline mutation status, morphological variant, Grade, receptor status (ER, PR, HER2neu).
- The frequency of germline mutations forming the familial breast cancer in Tatarstan and Bashkortostan republics.
- Proportion of different BC subtypes in both investigational and base groups.
- Demographic characteristics, familial and individual history for all the screened patients.

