## 1. INTRODUCTION

### 1.1 Background

Breast cancer (BC) occupies the first place among malignancy in females (29.9% of all tumors in female patients in Russian Federation in 2015) [1].

One of the most perspective direction of the oncotherapy is anticancer immunotherapy – employment of inhibitors of immune checkpoints. Immune checkpoints inhibitors (such as anti-PD-1 and anti-PD-L1 antibodies) have shown good clinical efficiency in clinical research to cure such malignant tumor with high mutation load, as melanoma, lung cancer, and others.

One of the hypothesis of such effect states that, usually, more cancer neoantigens are synthetized in the tumors with high mutation load (driven by genome instability), causing severe lymphoid infiltration [2-3]. This situation is balanced by overexpression of such inhibitors of the immune response as PD-1 and PD-L1 [4 - 6].

Breast cancer – is relatively heterogenic tumor, with different genetic, morphological and phenotypic forms.

Despite relatively low expression of PD-L1 in BC in general, there are reasons to believe that genetic instability, driven by mutations in genes involved in DNA repair, can increase the immunogenicity and, thus, the expression of PD-L1 in BC.

To date, it is widely accepted that 5-10% of BC cases are represented by hereditary types, i.e. mediated by germline pathogenic mutations in genes of DNA reparation pathways. Hereditary breast cancer (HBC), as well as ovarian cancer (OC), caused by mutations in genes BRCA1, BRCA2, CHEK2, TP53 и PTEN, and others. Thus, one of the promising directions here is to understand the inter-relation among germline pathogenic mutations associated with HBC, and activity of PD-L1. It would allow to optimize selection of anti-PD-L1 therapy, by forming group of patients (matching criteria of HBC) with high level of PD-L1 expression in cancer cells and tumor-infiltrating lymphocytes.

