### **2.2 Secondary objectives**

- To study the frequency of germline mutations forming the familial breast cancer in Tatarstan and Bashkortostan republics.
- To estimate the relation of the frequency of PD-L1 expression in tumor or/and immune cells with disease stage, receptor status (ER, PR, HER2neu), morphological type, Grade
- To estimate the relation of number of tumor-infiltrating lymphocytes (TILs) with disease stage, receptor status (ER, PR, HER2neu), morphological type, Grade and presence of clinically significant mutations in genes of DNA-repair system.

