### **13.3 Description of analysis sets**

All Enrolled set will consist of all the subjects who signed informed consent to enter the study. Patient disposition and baseline characteristics and demography as well as analysis of the primary and secondary objectives will be based on the set.

All patients will be enrolled in 2 groups 1:1. The analyses of primary objective will be conducted based on the results in these groups:

- The investigated group will be consists of patients with clinical features of hereditary BC (according to NCCN breast and/or ovarian cancer genetic assessment guidelines V1.2017) and revealed clinically significant (pathogenic) germline mutations in DNA-repair genes (TP53 MLH1 MSH2 MSH6 PMS2 EPCAM APC MUTYH CDKN2A CDK4 ATM KIT PDGFRA CDH1 CTNNA1 PRSS1 SPINK1 BRCA1 BRCA2 FANCI FANCL PALB2 RAD51B RAD51C RAD54L RAD51D CHEK1 CHEK2 CDK12 BRIP1 PPP2R2A BARD1 PARP1 STK11 XRCC3) regardless morphological type, grade, receptor status and extent of the disease.

- The control group will be consisting of patients with sporadic BC without germline mutations in DNA-repair genes (TP53 MLH1 MSH2 MSH6 PMS2 EPCAM APC MUTYH CDKN2A CDK4 ATM KIT PDGFRA CDH1 CTNNA1 PRSS1 SPINK1 BRCA1 BRCA2 FANCI FANCL PALB2 RAD51B RAD51C RAD54L RAD51D CHEK1 CHEK2 CDK12 BRIP1 PPP2R2A BARD1 PARP1 STK11 XRCC3) regardless morphological type, grade, receptor status and extent of the disease.

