## **14. DETERMINATION OF SAMPLE SIZE**

Today the data of PD-L1 expression level in breast cancer are limited. There are a few number of studies, which evaluated the frequency of PD-L1 expression in different breast cancer variants and the data of PD-L1 expression level in these studies are very differentiated depends on diagnostic approach, clone of antibodies and cut-off. We have calculated 2 variants of sample size based on minimal and maximal literature quantity data, using the Chi-squared statistic (or z test). Due to the absence of exact data about PD-L1 expression in hereditary and sporadic breast cancer we calculated the sample size based on data from general BC population (mainly is represented by sporadic BC) and TNBC (significant part of which is represented by hereditary BC). In the articles used as basis for calculation the authors assessed PD-L1 expression in tumor cells and the cut-off for PD-L1 positivity was 5%. In 2 studies estimated PD-L1 expression in total BC population as 4% and in TNBC as 11% the SP142 clone was used for IHC. We have found the only one study assessing concordance between SP142 and SP263 antibodies clones for IHC (on a subset of cases including BC) and the concordance was 95%. We are planning to assess the PD-L1 expression in both tumor and immune cells and use the 25% of PD-L1 positive cells as cut-off.

Considering the listed above we assume that the sample size will be near to a mean value between these two calculations.

Near 120 patients with breast cancer who have mutations in DNA-repair system genes and near 120 patients with breast cancer without mutations will be enrolled to the study in 2 centers:

Tatarstan Cancer Center, Kazan and Bashkortostan Clinical Oncology Center, Ufa. We will need to test near 390 patients for enrolling 240 patients (expected screen failure rate 35-40%). This data are based on the results of own pivotal study which has shown the frequency of clinically significant mutations in genes of DNA-repair system in familial BC 65%.

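### PD-L1 by receptor status and other tumour features is planned without a split by, or adjustment for, carrier group in a sample recruited 1:1 on carrier status, so the crude relations mix in the carrier effect

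*Combined protocol and SAP*

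**What the plan says.** - **Sampling.** Section 13.3: "All patients will be enrolled in 2 groups 1:1". Section 14 gives the sizes: "Near 120 patients with breast cancer who have mutations in DNA-repair system genes and near 120 patients with breast cancer without mutations".
- **Analysis set.** Section 13.3 defines the All Enrolled set as everyone who signed consent, and says that baseline description, "as well as analysis of the primary and secondary objectives will be based on the set". The two groups are then attached to one objective only: "The analyses of primary objective will be conducted based on the results in these groups".
- **Secondary PD-L1 objective.** Section 2.2: "To estimate the relation of the frequency of PD-L1 expression in tumor or/and immune cells with disease stage, receptor status (ER, PR, HER2neu), morphological type," and grade. Carrier status is not mentioned in it.
- **Secondary PD-L1 measures.** Section 13.2 lists PD-L1 high by morphological variant, and "Proportion of PD-L1 high cases in different receptor status (ER, PR, HER2neu) patients subgroups". Neither item is split by group. The same list does ask for tumour subtypes by group. Stage and grade for PD-L1 come only from section 2.2.
- **TILs.** Sections 2.2 and 13.2 both list germline mutation status among the factors to be related to TILs.
- **Model.** Section 13.4 names one model, a logistic regression of PD-L1 on mutation status. It gives no stratification, covariate or weighting for the secondary relations.
- **Background share.** Section 1.1: "5-10% of BC cases are represented by hereditary types".

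**The concern.** A tumour feature and PD-L1 will appear related in a pooled table if carrier status is related to both, even when they are unrelated among carriers and among non-carriers. The protocol supplies both links for triple-negative disease.

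- **Carrier group and PD-L1:** section 14 assumes 0.30 high in hereditary and 0.14 in sporadic disease.
- **Carrier group and receptor status:** section 14 says that much of triple-negative disease is hereditary, and uses triple-negative PD-L1 rates as a stand-in for the hereditary group. Attachment 3 lists triple-negative cancer by age 60 among the hereditary features that section 13.3 requires of the investigated group.

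Taking patients whatever their receptor status, as section 13.3 does, means that receptor status does not restrict entry. It does not balance receptor status between the groups.

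At stake is the answer to the second secondary objective. Section 1.2 wants the study to help identify patients who may respond to checkpoint inhibitors. A receptor-status relation that partly reflects the recruitment ratio could be taken for a tumour-biology finding.

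**Working it through.** **1. The plan's own figure.** Inputs (section 14, third scenario): P0 = 0.14, P1 = 0.30, two-sided alpha 0.05, power 80%, equal groups.

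- Pooled P = 0.22
- A = 1.960 × √(0.22 × 0.78 × 4) = 1.624
- B = 0.842 × √(2 × 0.30 × 0.70 + 2 × 0.14 × 0.86) = 0.684
- N = (1.624 + 0.684)² / 0.16² = 208, as stated
- Continuity correction = 1/(0.5 × 0.16) = 12.5, giving 104 + 13 = 117 per group, 234 in total, as stated
- Odds ratio = (0.30 × 0.86)/(0.14 × 0.70) = 2.633, as stated. (The printed RR of 2.114 should be 0.30/0.14 = 2.143; this has no bearing here.)

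So 0.30 and 0.14 are the rates on which the study is sized, and they are used below.

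**2. Set-up.** Let f be the carrier share of the sample, and t1 and t0 the triple-negative share in carriers and controls. Assume no receptor effect within either group. Then PD-L1 high is

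- triple-negative: [f·t1·0.30 + (1−f)·t0·0.14] / [f·t1 + (1−f)·t0]
- other tumours: the same with 1−t1 and 1−t0 in place of t1 and t0

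The documents give no values for t1 and t0. I assume t1 = 30-60% and t0 = 10-15%.

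**3. One case in full: 120 + 120 patients, t1 = 30%, t0 = 10%.**

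- Triple-negative: 36 carriers and 12 controls. (36 × 0.30 + 12 × 0.14)/48 = 12.48/48 = 26.0%
- Other: 84 carriers and 108 controls. (84 × 0.30 + 108 × 0.14)/192 = 40.32/192 = 21.0%
- Pooled odds ratio = (0.26 × 0.79)/(0.21 × 0.74) = 1.32, although it is 1.00 within each group

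**4. Pooled odds ratio over the assumed range, with an unselected series for comparison.** The 5% and 10% columns use the hereditary share in section 1.1.

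| t1, t0 | PD-L1 high in 1:1 sample, triple-negative v other | OR, 1:1 sample | OR, 5% carriers | OR, 10% carriers |
|---|---|---|---|---|
| 30%, 10% | 26.0% v 21.0% | 1.32 | 1.13 | 1.22 |
| 40%, 12% | 26.3% v 20.5% | 1.39 | 1.15 | 1.26 |
| 60%, 12% | 27.3% v 19.0% | 1.60 | 1.25 | 1.42 |
| 60%, 15% | 26.8% v 19.1% | 1.55 | 1.20 | 1.34 |

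At the two extreme corners, (30%, 15%) and (60%, 10%), the 1:1 odds ratio is 1.22 and 1.64; at 5-10% carriers it is 1.07-1.12 and 1.29-1.48. If t1 = t0, it is 1.00 in every column.

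**5. What stratifying does.** In this scenario the odds ratio in each group is 1.00, so a Mantel-Haenszel estimate, or a logistic model with a group term, returns 1.00.

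**The case against.** **The pooling is inferred.** Section 13.2 lists measures and never says that groups are combined. The sentence on the All Enrolled set also covers the primary objective, which is split by group, so naming a set does not forbid stratifying. A full SAP is promised before database lock. This is fair: the plan does not state outright that it will pool. But section 13.2 writes a group split where it wants one, section 13.3 ties the groups to the primary objective alone, and section 13.4 offers no adjustment. An analyst following the text would produce crude tables, and a later SAP does not change that text.

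**Part of the association is not due to the design.** A reader might put the whole pooled odds ratio down to 1:1 recruitment. An unselected series would also show about 1.1-1.4; recruitment multiplies this by roughly 1.1-1.3 (1.32/1.22 to 1.60/1.25). This stands.

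**The bias is small beside sampling error.** At 240 patients, approximate 95% intervals for the four odds ratios start at 0.64-0.86 and end at 2.7-3.0. This also stands, but the bias has a predictable direction under these assumptions and can be removed with data already collected.

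**TILs.** It is tempting to say that the TIL analyses ignore carrier status. They do not, since mutation status is a named factor and sections 3.1 and 13.2 contemplate TILs by group. The gap is only that no joint or within-group analysis is stated.

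**Population rates.** A reader might infer that pooled percentages will be passed off as breast cancer rates: 0.5 × 0.30 + 0.5 × 0.14 = 22%, against 14.8% at 5% and 15.6% at 10% carriers. The arithmetic is right, but the plan announces no such use; its objective is a relation.

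**Conclusion.** The point holds for PD-L1 by receptor status. As written, the crude tables mix a carrier effect into that relation, and equal recruitment of carriers and non-carriers makes the mixture larger than in routine patients. The size is a pooled odds ratio of about 1.3-1.6 (1.2-1.6 with the corners), against about 1.1-1.4 in an unselected series (1.1-1.5 with the corners) and 1.0 within groups. It rests on the plan's 0.30 and 0.14, on no receptor effect within groups, and on triple-negative shares that I have assumed.

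Four limits apply.

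- For morphology, stage and grade the same mechanism could operate, but the documents give no figures, so neither its presence nor its size can be shown.
- For TILs the size is unknown.
- The All Enrolled set is everyone who consented, and section 14 expects to test about 390 to enrol 240, so the pooled mix may not be exactly 1:1.
- The primary comparison is already between the groups, so nothing here counts against it.

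This is a cheap improvement to secondary analyses and should be made before database lock.

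**What to change.** In sections 13.2 and 13.4, and in the SAP, state that:

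1. PD-L1 high by stage, receptor status, morphology and grade is reported separately within the investigated and control groups.
2. Any single combined relation is estimated with group as a stratum (Mantel-Haenszel) or as a model term.
3. Relations of TILs with tumour features are estimated jointly with mutation status.
4. Any pooled percentage is labelled as describing the enriched sample.

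Reweighting the groups to a 5-10% carrier share is not advised. The groups are patients with hereditary features and a mutation, and sporadic patients without one. Patients with hereditary features but no mutation, and carriers without such features, belong to neither. The first kind is not rare on the protocol's figure of 65% mutation frequency in familial disease, which leaves 35%. No weighting of these two groups recovers a rate for breast cancer as a whole.

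The cost is wording and a few more tables, with no new patients or data. The real downside is small cells: in the first case worked above, the controls hold 12 triple-negative patients with 12 × 0.14 = 1.7 expected PD-L1 high. Within-group intervals will be wide, and some rows will support description only.
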